*2. What is/are the research question(s)/specific aim(s)? Pose very specific questions that can be addressed within the proposed design of the study. Prioritize them in order of importance.*

The specific aim of the study is to determine whether the use of perioperative IV TXA, given prior to incision (concurrent with preoperative antibiotics) and then at wound closure, reduces the calculated total blood loss postoperatively in patients undergoing PAO when compared to a patients receiving placebo (normal saline). A 250 mL difference in blood loss will be considered a clinically important difference [18].

Secondary objectives of the study are to study whether the use of IV TXA reduces intraoperative cell saver utilization, transfusion of allogeneic blood, and hospital length-of-stay (LOS) compared to placebo use. We will also compare complications between study groups, including the incidence of clinically apparent deep vein thrombosis (DVT) and pulmonary embolism (PE), from postoperative day zero through 6 weeks postoperatively.

3. *What is/are the hypothesis(es)?*

**Hypothesis 1:** The use of IV TXA given prior to incision and at the time of wound closure will decrease the postoperative calculated total blood loss in patients undergoing PAO compared to patients receiving placebo.

**Hypothesis 2:** Patients receiving perioperative IV TXA will have lower intraoperative cell saver utilization, lower rate of allogeneic blood transfusion, shorter hospital LOS after PAO compared to patients receiving.

**Hypothesis 3:** There will be no difference in the rate of symptomatic venous thromboembolic events (VTE) (i.e., DVT and PE) in the 6 weeks after PAO surgery in patients who receive perioperative IV TXA compared to patients receiving placebo.

4. *Identify and define the primary outcome and when the outcome will be measured. If measuring change in post-operative function is the most important, that will be your primary outcome.*

Postoperative calculated total blood loss after PAO, determined from estimated blood volume [19], change in postoperative hemoglobin (preoperative hemoglobin – final inpatient hemoglobin), and transfused hemoglobin [20,21].

5. *Identify and define the secondary outcome(s) and when they will be measured (list additional goals one at a time with their corresponding outcomes).*

Secondary outcomes:

1. Intraoperative cell saver utilization: cumulative mL of reinfusion, measured at the end of the case intraoperatively

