2. Postoperative allogeneic transfusion (units of packed red blood cells per patient)
3. Length of hospital stay (postoperative day of discharge after surgery)
4. Incidence of complications at 6 weeks postoperatively, specifically:
  - VTE (symptomatic of DVT or PE)
  - Infection (superficial, deep)
  - Hematoma
  - Seroma
  - Reoperation

Patients will not be followed longer than 6 weeks during this trial, as we are aware of no evidence to suggest that TXA will influence outcomes outside of the perioperative period.

The authors will create a data safety monitoring board (DSMB) that will meet once a quarter to capture any complications, including but not limited to: death, DVT, PE, and wound complications.

This will include anesthesia, surgical, nursing, and research representatives. The time frame for reporting adverse events will be 1 week. If any mortality is seen, or any increase in DVT or PE rates from the established incidence in the literature (i.e., 0.94% for symptomatic VTE), the study will be stopped. The senior author and principal investigator will contact the IRB directly if any of the above occurs. In accordance with the Hospital guidelines for TXA use, DVT, PE, stroke, transient ischemic attack (TIA) and myocardial infarction (MI) will be reported to the Department of Quality Management ([name]).

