**Data recorded from the electronic medical record will include:**

- Date of surgery
- Patient age at the time of surgery
- Patient gender
- Patient height (cm) and weight (kg) at time of admission

- Transfusion requirement during inpatient stay (units required)
- Postoperative day and time of discharge
- Preoperative CBC data and coagulation study data
- Postoperative hemoglobin on all inpatient days postoperatively (g/dL)
- Chart review of progress notes for evidence of clinically significant VTE
- Chart review of progress notes for evidence of reoperation, hematoma, seroma, or postoperative infection

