**Data recorded from outpatient postoperative office records will include:**

- Chart review of progress notes for evidence of clinically significant VTE
- Chart review of progress notes for evidence of reoperation, hematoma, seroma, or postoperative infection
- Chart review of progress notes for documentation of reoperation

c) *If controls are included in this proposal, please include the following: describe how they will be matched with the study subjects; state whether the controls will have identical data recorded, or describe any differences compared to the intervention subjects.*

Patients will be randomized to either the intervention or control group, as per randomization protocol described elsewhere in the proposal. For patients who are randomized to the control group, study data will be collected in the same manner as for the intervention group.

e) *Are all the tests or images part of standard of care? If not, identify which tests are not standard of care. What source of funds will be used to pay for them?*

All tests and imaging are considered standard of care.

e) *Create a data collection sheet and include all data/datafields to be collected. Include time points of data collection and final outcome time point. Attach the data collection sheet.*

Please see attached.

f) *Attach/upload all questionnaire(s) to be used. Provide information about the validity, reliability and appropriateness of the instrument(s) for your study.*

g) If randomization is involved, state how the randomization will be done, by whom, when, who will ensure randomization is carried out, and whether anyone will be blinded to the randomization group. Clearly explain the treatment arms of the study.

*Randomization Process:*

The patients will be randomized into one of 2 groups: (1) 10 mg/kg, up to a maximum of 1 g, of IV TXA (diluted in 50 mL of normal saline, with a maximum concentration of 100 mg/mL) or (2) 50 mL of normal saline prepared by the pharmacy. Assignment of patients will be made prior to the initiation of enrollment for the study. Patients will be randomized using a computer generated (SAS PROC) block randomization schedule to ensure equivalent numbers of patients in each group over the course of the study in case early stopping is required. Randomization will be stratified by sex and surgery type (PAO or Scope/PAO) so that the number of male patients and Scope/PAO patients will be balanced in each study group between trial arms.

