The authors will create a data safety monitoring board (DSMB) that will meet once a quarter to capture any complications, including but not limited to death, DVT, PE, and wound complications. This will include anesthesia, surgical, nursing, and research representatives. The time frame for reporting adverse events will be 1 week. If any mortality is seen, or any increase in DVT or PE rates from the established incidence in the literature, the study will be stopped. The senior author and principal investigator will contact the IRB directly if any of the above occurs. In accordance with the Hospital guidelines for TXA use, DVT, PE, stroke, transient ischemic attack (TIA) and myocardial infarction (MI) will be reported to the Department of Quality Management ([name]).

One planned interim analysis for efficacy will be performed after outcome data are collected on 50% of patients. The Haybittle-Peto boundary will be employed, where the DSMB will consider stopping the trial if the independent samples t-test comparing calculated blood loss volume between the TXA and placebo groups produces a p-value  $< 0.001^1$ . If the trial continues to completion, the final p-value threshold for significance will be the typical 0.05. No adjustment in sample size is necessary to account for the interim analysis.

Upon completion of the study, the results will be reported according to the CONSORT guidelines.

You have completed the Clinical Research Proposal for this study. The proposal should be submitted to the appropriate Clinical Review Panel (CRP) for scientific review. If you are unsure of which Clinical Review Panel to select, please contact [name] at [name].

 Pocock SJ. When (not) to stop a clinical trial for benefit. JAMA 2005; 294:2228-20.

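### Stroke, TIA and MI are reportable under the hospital TXA guidelines but are missing from the 6-week complication outcome and the written data lists, so the prespecified thrombotic safety result is venous only

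*Combined protocol and SAP*

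**What the plan says.** The DSMB paragraph in Section A, question 5, ends: "In accordance with the Hospital guidelines for TXA use, DVT, PE, stroke, transient ischemic attack (TIA) and myocardial infarction (MI) will be reported". Section D repeats this and gives the recipient: "DVT, PE, stroke, transient ischemic attack (TIA) and myocardial infarction (MI) will be reported to the Department of Quality Management". Stroke, TIA and MI appear nowhere else in the supplied text.

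The complication outcome (Section A, question 5, item 4) is introduced by "Incidence of complications at 6 weeks postoperatively, specifically". Five entries follow: "VTE (symptomatic of DVT or PE"), infection, hematoma, seroma and reoperation. Hypothesis 3 (Section A, question 3) is also confined to venous events: "There will be no difference in the rate of symptomatic venous thromboembolic events (VTE) (i.e., DVT and PE) in the 6 weeks after PAO surgery".

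The medical-record list in C.3(b) asks for "Chart review of progress notes for evidence of reoperation, hematoma, seroma, or postoperative infection" and, separately, for VTE. The office-record list asks for "Chart review of progress notes for evidence of clinically significant VTE" and the same non-thrombotic complications. The radiology list covers VTE, hematoma and seroma. The operating-room list has no complication field.

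The stopping sentence, given in both sections, begins "If any mortality is seen, or any increase in DVT or PE rates". The next sentence requires IRB contact by referring back to what precedes it. Stroke, TIA and MI are named only after that.

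Other provisions are wider. The DSMB's remit is open-ended and names death. C.3(a) provides for a general review of inpatient and office records for complications. Section A, question 2, commits to comparing complications between groups, with DVT and PE given as inclusions. Adverse events in general have a 1-week reporting time frame.

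**The concern.** The plan itself treats arterial thrombotic events as relevant to TXA. It lists them for reporting, and C.2 excludes patients with coronary stents or known coronary disease. It also aims to supply Level I evidence for a drug that it expects to be safe. Yet the outcome that will carry the safety comparison defines thrombosis as DVT and PE.

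At stake is what the trial can say at the end. A non-fatal stroke or MI in either arm has a defined route to a hospital department. It has no defined route to the trial dataset and no place in the prespecified complication table. A report that complications did not differ would then rest, for thrombosis, on venous events alone, and a reader could take it to mean more.

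**Working it through.** The plan gives no figure on this point, so the main check is to set the provisions side by side. The sample size (40 per arm, 80 in total) is used only for scale and is not disputed. With a 250 mL difference, SD 383.27 mL and two-sided alpha 0.05, the exact t-test power at 40 per arm is 82.1%, matching the stated 82%.

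**Where each event appears**

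| Provision | DVT/PE | Stroke/TIA/MI | Death |
|---|---|---|---|
| Quality-department reporting (A.5, D) | named | named | not named |
| Hypothesis 3 (A.3) | named | absent | absent |
| 6-week complication outcome (A.5, item 4) | named | absent | absent |
| Medical-record list (C.3(b)) | VTE | absent | absent |
| Operating-room list (C.3(b)) | absent | absent | absent |
| Radiology list (C.3(b)) | VTE | absent | absent |
| Office-record list (C.3(b)) | VTE | absent | absent |
| Stopping trigger (A.5, D) | named | absent | named |
| DSMB remit (A.5, D) | named | not named, but remit open | named |

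Three of the five reportable event types (3/5) are absent from the outcome, all four written lists and the named stopping trigger. Section D reports the incidence of complications as proportions with 95% confidence limits, and the only itemised definition of that outcome is the closed list in A.5.

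**Scale, if the events were added**

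With zero events in n patients, the two-sided 95% Clopper-Pearson upper limit is 1 − 0.025^(1/n):
- n = 40 (one arm): 8.8%
- n = 80 (both arms): 4.5%

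The documents give no arterial event rate. For an assumed per-patient risk p, the chance of at least one event in 80 is 1 − (1 − p)^80:
- p = 0.1%: 7.7%
- p = 0.5%: 33.0%
- p = 1%: 55.2%

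The counts could therefore only be described. Over this assumed range, seeing at least one event runs from unlikely to slightly more likely than not.

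**The case against.** The strongest reply is that nothing is really lost. The DSMB is to capture complications without limit to those named, and a stroke or MI is plainly one. Records are to be searched for complications generally. The between-group objective in A.2 is worded openly, and results will follow CONSORT. The population is aged 12 to under 45, with coronary disease and prior thromboembolism excluded, so events should be rare and no planned test or sample size would change.

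Much of this stands, and it rules out several stronger readings that a reader might infer:

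- **That the whole safety result is venous only.** Infection, hematoma, seroma and reoperation are also complication outcomes. Only the thrombotic part is venous only.
- **That no collection form looks for these events.** C.3 refers to attached data collection sheets that were not available. The statement holds only for the lists written in C.3(b).
- **That the DSMB would not see a stroke or MI.** Its open remit and the record review could both pick one up.
- **That the IRB would not be told.** The IRB sentence refers back to preceding text that includes the DSMB's general remit as well as the stopping trigger. Its reach is ambiguous; an exclusion is not shown.
- **That deaths would go uncounted.** Death is in the DSMB remit and any mortality triggers stopping, which would include a fatal stroke or MI.

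What the reply does not supply is a named field, or a commitment to tabulate non-fatal stroke, TIA or MI by arm. Ad hoc capture leaves both to chance. Rarity is a reason to count descriptively; it is not a reason to leave the events undefined.

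**Conclusion.** The concern holds in a limited form. Non-fatal stroke, TIA and MI are named as reportable but have no place in the closed 6-week outcome, the written data lists or the named stopping trigger, so the prespecified thrombotic safety result covers DVT and PE only. The size is three of five named event types. The effect is on the completeness and interpretation of the safety report; the primary analysis and its power are untouched.

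This rests on two assumptions: that the unavailable collection sheets follow the written lists, and that the closed list in A.5 defines the complications analysed in Section D. If the sheets already carry these fields, what remains is to align the protocol text with them. The documents do not support a claim that such events would escape all monitoring.

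**What to change.** 1. Add stroke, TIA and MI to the 6-week complications in Section A, question 5, item 4, and to the medical-record and office-record chart-review lists in C.3(b). Check that the attached collection sheets match.
2. In Section D, report them as descriptive counts by arm alongside the other complications, with no hypothesis test.
3. State that events sent to the Department of Quality Management also go to the DSMB and the trial dataset, within the existing 1-week time frame for adverse events.
4. The sponsor and DSMB should reconcile the reportable-event list with the stopping and IRB sentences in Sections A and D, and say what the IRB sentence's back-reference covers. No stopping rule is proposed here.

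The cost is a few lines on the collection sheet, short edits to the protocol text, and slightly more chart-review and reporting work. The same charts are already being read, so no new tests, visits or patients are needed.

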**B. BACKGROUND – why are these questions important to answer? Be sure to answer each question individually.**

*1. Explain why these research questions are being asked.*

The use of tranexamic acid is gaining popularity as a method to reduce blood loss and transfusion rates in a variety of orthopedic procedures [22]. Multiple randomized studies and subsequent meta-analyses have shown that intravenous tranexamic acid is effective at reducing blood loss and transfusion rates as well as overall hospital costs in elective orthopedic surgery [5-10, 23,24]. In addition to the risks of surgery, blood transfusions are also associated with risks including prolonged hospital stay, increased cost, transmission of blood-borne infections, transfusion-related reactions (acute hemolytic reactions, febrile non-hemolytic reactions, allergic reactions including anaphylaxis, and graft versus host disease), transfusion-related acute lung injury, circulatory overload, immune-mediated transfusion effects, and hardware infections [21, 25-29].

Periacetabular osteotomy requires multiple pelvic osteotomies around the acetabulum [1], which can result in clinically significant blood loss, necessitating allogeneic transfusion in up to 58% of cases [2,11]. In our experience, the average calculated total blood loss for PAO is  $1.30 \pm 0.38$  L (range, 0.32 L – 2.65 L), and 33.3% of our patients have required transfusion of at least one allogeneic unit of blood postoperatively (our unpublished data). There has been only one retrospective study examining the effect of IV TXA on blood loss and transfusion after PAO [11]. The results were promising, demonstrating a 30.8% reduction in total blood loss ( $p=0.001$ ) and a 58.6% reduction in transfusion rate ( $p=0.013$ ) [11].

Despite theoretical concern that TXA may increase the risk of VTE, a 2011 Cochrane review assessing 252 randomized controlled trials and over 25,000 patients treated with antifibrinolytics concluded that there is no evidence that TXA increased morbidity or mortality [24]. Furthermore, the established risk for clinically significant VTE after PAO is low: 0.94% [30]. Therefore, we believe that IV TXA may be an effective, inexpensive and safe intervention to decrease postoperative blood loss in patients undergoing PAO. The goal of this study is to provide Level I evidence to support TXA use during PAO.

*2. What is the background of the topic that you believe is important for the reviewer to know in considering this protocol, including prior studies by this research team. Describe strengths and deficiencies of prior studies; explain how this study fits in. Include references.*

No Level I evidence exists regarding the use of IV TXA during PAO. To our knowledge there is only one prior study (published as an abstract) of IV TXA in the PAO patient population [11]. The authors retrospectively analyzed two longitudinal cohorts before and after implementation of an IV TXA protocol. All 100 patients received PAO performed by a single surgeon. Total blood loss was

706.16mL versus 1020.6 mL (p=0.001), for the TXA group compared to the non-TXA group, respectively. The study also showed a decrease in transfusion rate from 58% to 24% with the use of tranexamic acid, with the mean number of units transfused decreasing from 1.02 to 0.28 (p=0.013). This study did not find an increased incidence of VTE associated with the use of tranexamic acid [11]. The primary weakness of this study is its design. It was retrospective comparative study, with unmatched cohorts. Thus, it provides Level III evidence.

3. *Identify specific gaps in current knowledge that this study is intended to fill.*

Multiple well-done studies and meta-analyses have shown that intravenous (IV) of TXA reduces postoperative bleeding and the need for transfusion after major orthopedic surgery, without demonstrably increasing the risk for postoperative complications, including venous thromboembolic events (VTE) [5-10]. However, there are no high-level studies of IV TXA during PAO. We intend to provide the Level I evidence in support of the use of IV TXA for this indication.

4. *How will answering these questions change clinical practice, change concepts about the topic or confirm the work of other investigators?*

We hypothesize that our results will confirm the work of Wingerter, et al [11]. If the use of IV TXA in the PAO patient population significantly reduces total blood loss, then it would provide an efficacious and inexpensive method for reducing postoperative morbidity after PAO.

5. *Is this a pilot study that could lead to a more definitive protocol or different study?*

No.

#### C. METHODS – STUDY DESIGN AND PLAN

##### 1. What is the Study Design – choose whatever is appropriate

###### Observational:

- Case Series – description of a series of cases (e.g., the first 20 of a new procedure). This often results in a technique paper, but does not require hypothesis testing or measurement of objective outcomes.
- Cross-sectional Study – data is obtained at a single point in time and reflects patients' current condition. It is like taking a single snapshot of a group of patients. All data are collected at one time point without follow-up (e.g., a survey of surgical satisfaction at one year).
- Retrospective Study – a retrospective review of a cohort of patients with a specific characteristic based on a stated hypothesis (e.g., all total shoulder replacements performed at HSS over a 5 year period to examine the risk factors for DVT). This includes evaluation of patient records and documentation and does not require patient consent. These studies are conceived after data has been collected. Retrospective reviews of data in a Registry or material in a Tissue Repository fall under this category.
- Retrospective Study with Follow-up – A retrospective review of a cohort of patients with a specific characteristic based on a stated hypothesis (see above example). This includes evaluation of patient records and documentation, as well as patient contact for follow-up. This type of study requires patient consent. These studies are conceived after data has been collected or in combination with some prospective data collection.
- Prospective Cohort Study – a prospective evaluation of a cohort of patients with a specific characteristic over time to see if they develop a particular endpoint or outcome based on a stated hypothesis (e.g., establishing a cohort to follow patients undergoing a novel procedure in order to evaluate pre- and post-operative function/pain). These studies are conceived before data is collected.

Registry – by nature a prospective cohort study, but one in which the data is warehoused for the purposes of studying many hypotheses with the same patient population and collected continuously, usually for a long period of time.

Case-control Study – compares “cases” (those with a condition or procedure of interest) with “controls” (those without the condition or procedure of interest) to assess risk factors (e.g., total shoulder patients with post-op DVT compared to an age and sex matched control group of total shoulder patients without post-op DVT). Cases are identified first and then controls are identified that represent an appropriate comparison group – they would have been cases if they’d had the condition or procedure of interest.

Validation Study – A study designed to test the validity, reliability, repeatability of a diagnostic test or outcome measurement (e.g., comparing a new function or test to the gold standard). These studies do not study the patient’s health directly, but rather evaluate the quality of tests done to study the patient’s health.

Other – please describe:

